4.4 Discontinuation/Withdrawal of Study Participants

A participant will be considered to have completed the study when he/she completes all scheduled study treatments and follow-up visits. If a participant discontinues the study at any time after dosing, the investigator will make every effort to have the participant complete all assessments as indicated in Section 7.1 – Safety Parameters. The investigator will make every effort to have all scheduled immune assessment blood samples collected as indicated in the Schedule of Events, **Table S2**.

Unless a participant refuses to continue participation, all follow-up visits and procedures should be completed as indicated in the Schedule of Events, **Table S2**, following the last dose whether or not the participant has completed all doses.

The reason for any discontinuation of investigational product will be discussed with the Sponsor's Medical Monitor and indicated on the study forms. The primary reason for a participant discontinuing further dosing or withdrawal from the study itself is to be selected from the following standard categories:

- **Adverse Event (Adverse Reaction)**: Clinical or laboratory events occurred that, in the medical judgment of the investigator, are grounds for discontinuation for the best interest of the participant. This includes serious and non-serious adverse events regardless of relation to study drug.
- **Death**: The participant died.
- **Withdrawal of Consent**: The participant desired to withdraw from further participation in the study in the absence of an investigator-determined medical need to withdraw. If the participant gave a reason for withdrawal, it must be recorded on the case report form (CRF). This reason does not allow for further data collection or later study related procedures.
- **Protocol Violation**: The participant failed to meet the protocol entry criteria or failed to adhere to the protocol requirements (e.g., treatment noncompliance, failure to return for defined number of visits). The violation should be discussed with the Sponsor's Medical Monitor prior to discontinuation of either study treatments or study withdrawal.

- Lost to Follow-up: The participant fails to attend study visits and study personnel are unable to contact the participant after repeated attempts including letter sent by certified mail or its equivalent.
- Physician Decision: The participant was terminated for a reason other than those listed above by the physician caring for the participant.
- Other: The participant was terminated for a reason other than those listed above, such as termination of study by the Sponsor.

5. STUDY PRODUCT

5.1 Investigational Product

GLS-5700, the investigational product to be used in this study, contains a DNA plasmid encoding for the pre membrane and envelope (prME) proteins of Zika virus and is formulated in sterile salt citrate buffer (SSC). GLS-5700 will be provided (**Table 5.1**) at a concentration of 10 mg/ml.

Table 5.1: Investigational Product

GLS-5700	
Recoverable volume per container	0.4 mL minimum
Concentration	10 mg/mL
Container Size and Type	2 mL glass vial

5.2 Packaging and Labeling of GLS-5700

Study product will be supplied in a non-blinded fashion. Study product will be shipped directly from the manufacturer or its designee to the study site. Each vial will be labeled with a single panel label (**Table 5.2**).

Table 5.2: Sample labels for the final drug product components

Biologic Product/ Diluent	Sample Label
GLS-5700 / SSC	GLS-5700 [10 mg/ml] 0.4 mL/Vial Single Use Vial Lot: GLS-5700.xxxxx Date of Manufacture: DD MMM YYYY Final Retest Date DD MMM YYYY Store at 2 - 8°C CAUTION New Drug – Limited by Federal Law to Investigational Use GeneOne Life Science, Inc. Rev 000

5.3 Handling of GLS-5700

Study product accounting will be performed continuously during the study. Details on study product volume, administration, and accountability are documented in the CRF and on respective pharmacy forms. At completion/termination of the study, all unused and partially used supplies must be returned to GeneOne Life Science, Inc. The investigator, pharmacist/drug administrator and monitor must verify that no drug supplies remain at the site at the time of study close-out. Appropriate records will be maintained in the investigator's site file.

GeneOne Life Science, Inc. will be responsible for assuring the quality of the investigational product is adequate for the duration of the trial. GLS-5700 will be shipped refrigerated. If there the cold packs are at room temperature when the shipment is received, the Sponsor must be contacted immediately.

Investigational product(s) must be stored in a secure area according to local regulations. All study products must be transferred from the shipping container to the appropriate storage conditions upon arrival. GLS-5700 must be stored refrigerated at 2 to 8°C.

Refrigerator/freezer temperature logs must be maintained at the clinical site and temperatures must be recorded and monitored regularly.

5.4 Dispensing of GLS-5700

It is the responsibility of the Investigator to ensure that GLS-5700 is only dispensed to study participants. Authorized personnel at the official study site must be the only ones to dispense the product according to local regulations.

The dosing syringe must be labeled with a four-hour expiration date from the time the vial(s) are removed from storage.

Detailed instructions on handling and dispensing of Investigational Product are provided below.

5.5 Precautions with Investigational Medicinal Product

A dose of the study product known or suspected to have been taken (accidentally or intentionally) in excess of the dose mandated by the protocol, and any misuse or abuse of study products or any other product taken as a concomitant medication, whether or not associated with an adverse experience, must be reported to GeneOne Life Science within 24 hours. Any clinical sequelae in association with the overdose will be reported as an AE or SAE. Details of signs or symptoms, clinical management, and outcome should be reported, if available.

5.6 Preparation of Investigational Product

GLS-5700 is supplied in single dose 2 mL vials at a concentration of 10 mg/mL at a minimum recoverable volume of 0.4 mL. GLS-5700 is formulated in SSC.

Study drug is to be prepared by site staff who are trained and knowledgeable in mixing and dispensing investigational agents. Documentation of certification will be kept with the pharmacy documents. Study drug should be diluted and prepared in a BioSafety level 2 cabinet. Personnel will wear safety glasses, gloves and lab coat.

Remove investigational product from the refrigerator. Briefly centrifuge the vials between 500-2500 rpm for 3-5 seconds to remove any vaccine from the cap to the bottom of the vials. After centrifugation, maintain the vials in an upright position until use.

5.6.1 Preparation of 1 mg ID Dose

To prepare study drug for 1 mg ID dose, the pharmacy staff should have a 1 mL tuberculin syringe with 25 or 27 gauge needle. Label syringe as “1 mg GLS-5700

Dosing". Withdraw 0.20 mL of study drug (at 10mg/mL) into the syringe and prime to 0.1 mL.

5.6.2 Preparation of 2 mg ID Dose

To prepare study drug for 2 mg ID dose, the pharmacy staff should have two 1 mL tuberculin syringes with 25 or 27 gauge needles. Label both syringes as "2 mg GLS-5700 Dosing". Withdraw 0.20 mL of study drug (at 10mg/mL) into each of the two syringes and prime to 0.1 mL.

Additional instructions for Investigational Product preparation are provided in the Pharmacy Manual.

5.7 Records of Investigational Product Disposition at Site

It is the responsibility of the Investigator to ensure that a current record of investigational product disposition is maintained at each study site where investigational product is inventoried and disposed. Records or logs must comply with applicable regulations and guidelines, and should include:

- Amount received and placed in storage area;
- Amount currently in storage area;
- Label ID number or batch number and use date or expiry date;
- Dates and initials of person responsible for each investigational product inventory entry/movement;
- Amount dispensed to each participant, including unique participant identifiers;
- Amount transferred to another area/site for dispensing or storage;
- Amount returned to Sponsor;
- Amount destroyed at study site, if applicable.

5.8 Return and Destruction of Investigational Product

Upon completion or termination of the study, all unused and/or partially used investigational product must be returned to GeneOne Life Science, Inc., or its designee, if not authorized by GeneOne Life Science, Inc. to be destroyed at the site.

All investigational products returned to GeneOne Life Science, Inc., or its designee, must be accompanied by the appropriate documentation. Returned supplies should be in the original containers. It is the Investigator's responsibility to arrange for disposal for all empty containers, provided that procedures for proper disposal have been established according to applicable federal, state, local and institutional guidelines and procedures, and provided that appropriate records of disposal are kept. The return of unused investigational product(s) should be arranged by the responsible Study Monitor.

If investigational products are to be destroyed on site, it is the Investigator's responsibility to ensure that arrangements have been made for the disposal, written authorization has been granted by GeneOne Life Science, Inc., or its designee, procedures for proper disposal have been established according to applicable regulation and guidelines and institutional procedures, and appropriate records of the disposal have been documented. The unused investigational products can only be destroyed after being inspected and reconciled by the responsible GeneOne Life Science, Inc. employee or

designated Study Monitor. Used investigational product must NOT be destroyed until accountability has been completed by the responsible GeneOne Life Science employee or designated Study Monitor.

5.9 Use of CELLECTRA® Electroporation Device

Instructions for use of the CELLECTRA® device are located in the Operations Manual. Each clinical site will receive training for the use of the CELLECTRA® device. The following specifications will be used during the study:

CELLECTRA® 3P-ID

Number of pulses per treatment = 4

Maximum Current Strength = 0.2 Amperes

Voltage Strength = 1 - 200 Volts

Electroporation pulse duration = 52 milliseconds/pulse

Interval separating pulses = 1 second

EP needle array length (injection depth) = 3 mm (with array guide in place)

The **treatment/electroporation procedure** must be performed by qualified personnel. Any individual designated to perform the procedure should be permitted by the relevant local authorities to administer vaccinations or parenteral drugs to patients (e.g. MD, DO, RN). Non-licensed individuals (i.e., other than an MD, DO, or RN) may perform the treatment/electroporation procedure under both of the conditions below:

1. The non-licensed individual has been trained by the PI, approved Sub-Investigator, or sponsor in EP. The non-licensed individual will perform the procedure under the direct supervision of the Principal Investigator or an approved Sub-Investigator who has already been trained by sponsor personnel.
2. The CV and any relevant qualifications of the individual have been reviewed and approved by the sponsor or its designee to perform the procedure.

All individuals designated to perform the EP procedure must satisfactorily complete device training from the sponsor or its designee regardless of their qualifications. Any deviation from the above procedures must be approved by the sponsor or its designee.

5.10 Investigational Device Accountability

Each clinical site is responsible for maintaining investigational device accountability. This includes recording the CELLECTRA® serial number, applicator serial number, and array lot number used for treatment/ EP of each participant.

6. STUDY PROCEDURES AND TREATMENTS

See **Table S2** in the Clinical Protocol Synopsis for Schedule of Events showing study procedures and the times at which they are to be carried out.

6.1 Procedure by Visit

6.1.1 Screening Evaluations

The assessments during the screening phase will determine the participants' eligibility for the study and also their ability to comply with protocol requirements by completing all screening assessments. The following additional screening evaluations will be performed within 30 days prior to dosing on Day 0. All screening assessment values must be reviewed prior to study treatment.

- o Signed informed consent (Section 6.2.1);
- o Review and confirm all inclusion/exclusion criteria (section 4.2, 4.3);
- o Collect demographics, including gender, ethnic origin, and travel history;
- o Obtain complete medical history (including procedures history), present conditions and concomitant illnesses, and travel history (Section 6.2.2);
- o Record concomitant medications/treatments at present and in past 8 weeks;
- o Record vital signs (heart rate, blood pressure, oral temperature), body weight, height, heart rate (HR), blood pressure (BP), and oral temperature (Section 6.2.3.3);
- o Collect blood for CBC with differential, blood chemistry [Sodium (Na), potassium (K), chloride (Cl), bicarbonate (HCO₃), glucose, BUN, creatinine, AST, ALT, CPK (Section 6.2.3.6);
- o Collect blood for serologic assessment of HIV, Hepatitis B surface antigen (HBsAg), Hepatitis C antibody (HCV), and dengue, West Nile, and chikungunya virus antibodies
- o Serum pregnancy (Section 6.2.3.6);
- o 12 lead ECG (Section 6.2.3.5);
- o Physical Exam (Section 6.2.3.2); and
- o Determine proposed site of injection(s)

6.1.2 Study Evaluations

6.1.2.1 Vaccine Administration Visits

The following procedures will be performed at vaccination visits:

The following study evaluations will be performed **prior to dosing**:

- o Review of medical history from screening
- o Concomitant medications/treatments;
- o Vital signs;
- o Urine pregnancy test, if applicable
- o Collect blood for serum or PBMCs for immune assessment as indicated;
- o Targeted physical assessment
- o Adverse event assessment

Administer study treatment followed by EP

The following study evaluations will be performed **post dose**:

- o Pain assessment immediately and 30 minutes after EP;
- o Injection site reaction assessment 30 minutes after EP;
- o Distribute Participant Reminder Diary;
- o Download EP data from device as directed and forward to GeneOne Life Science or its designee

6.1.2.2 Telephone assessment (Day 1 post 1st vaccination)

The following procedures will be performed the day following the 1st vaccination:

- o Contact the study participant (either by phone or in person);
- o Local and systemic injection site review;
- o Adverse and Serious adverse event assessment;

6.1.2.3 Non-vaccination study visits

The following procedures will be performed during non-vaccination visits:

- o Concomitant medications/treatments;
- o Vital signs;
- o Targeted physical assessment;
- o Local and systemic injection site review;
- o Adverse and Serious adverse event assessment;
- o Collect blood for serum or PBMCs for immune assessment as indicated;
- o Collect blood for safety laboratory assessment (CBC, serum chemistries, CPK) [as indicated]
- o Review Participant memory aids [as indicated]

6.1.2.4 End of Study Visit (Week 60) / Early Termination

The following procedures will be performed 12 months after the end of treatment (week 60 visit):

- o Concomitant medications/treatments;
- o Vital signs;
- o Full physical exam;
- o Local and systemic injection site review;
- o Adverse event assessment;
- o Collect blood for serum or PBMCs for immune assessment as indicated;

6.1.2.5 Premature Withdrawal

Participants may refuse further vaccinations and/or terminate participation in the study at any time. In the event a participant decides to terminate participation prematurely, efforts should be made to perform all study

assessments. Participants may also discontinue participation in the study or have their participation discontinued by the principal investigator if safety and/or tolerability issues are considered intolerable and/or not manageable with symptomatic treatment.

At a minimum, all assessments from Week 14 visit should be performed prior to withdrawal if not already completed.

In the case of a fatal outcome, all relevant information (including cause of death, concomitant medication, and relationship to study treatment or underlying disease) will be collected.

6.2 Timing and Evaluations

6.2.1 Informed Consent

Study personnel will meet with prospective study participants, explain the study, and provide them with an informed consent form (ICF) that describes the screening tests, eligibility criteria for entering the study, and study treatments and follow-up procedures. An informed consent must be signed prior to any study related procedures being performed. A copy of the signed and dated consent form will be given to the participant.

6.2.2 Patient Identification Number and Group Assignments

Each participant who consents will be assigned a unique participant identification designation number (PID#), which identifies the participant for all study-related procedures that occur prior to receiving an allocation number. Once assigned, PID numbers cannot be reused for any reason. Information regarding participant's PID# and screen date will be documented on a screening log.

Study participants will be allocated to each of the two dosing groups such that the initial 5 eligible participants at each of the three study sites will be assigned to Group 1 at 1 mg/dose, the next 5 eligible participants at each study site will be assigned to Group 2 at 2 mg/dose. The final study participants will be allocated to the three study sites with 5 participants assigned to the 1 mg/dose group and allocated in a proportional manner between sites and the final 5 participants assigned to the 2 mg/dose group and similarly allocated in a proportional manner between study sites. Sponsor reserves the right to revise allocations between study sites should unexpected delays occur or any site cannot meet recruitment goals.

Medical History

Investigators should document all significant illnesses that the participant has experienced as Medical History. Illnesses' first occurring or detected during the study and/or worsening of an existing illness(es) that occur after the first vaccination are to be documented as AEs on the CRF. Prior treatments, defined as administered up to 8 weeks prior to the time of informed consent, will be recorded in the CRF as prior medications. Concomitant treatments, defined as continuing

or new treatments taken at or after the signing of the informed consent, will be recorded in the CRF as concomitant medications.

Travel History

Investigators should inquire as to travel to any country or region to include the South Pacific Islands, South America, Central America, or the Caribbean.

6.2.3 Safety Assessments

The following patient evaluations for safety will be performed.

6.2.3.1 Patient self-evaluations

Participants record any post treatment reactions (local and systemic) and enter this information in the Post Vaccination Memory Aid (shown in Appendix A) on the evening of each dose and for 7 days post each dose. Local administration site reactions will be recorded using the supplied measuring tool. The study staff will review the memory aid; the reported events will be assessed for clinical significance and recorded on the CRFs as appropriate. Memory aids are considered the property of the participants and are not collected nor considered as source documents.

Study staff should evaluate each unique memory aid entry according to “Toxicity Grading Scale for Healthy Adult and Adolescent Volunteers Enrolled in Preventive Vaccine Clinical Trials”, issued in September 2007 (Appendix B). Any memory aid entry determined to meet the criteria for a Grade 1 or higher adverse event must be documented as an adverse event. If the reminder diary entry does not meet the criteria of a Grade 1 or higher AE as per the toxicity grading scale, clinical judgment can be used to determine whether the entry should be recorded as an AE. For cases where the reminder diary entry and final AE reporting (i.e., grading) do not agree, the reasoning must be recorded in the source documents.

6.2.3.2 Physical Assessments and Targeted Physical Assessment

A full physical examination will be conducted at screening. A targeted physical assessment will be performed at other visits as determined by the Investigator or directed per participant complaints. The injection site is to be assessed by the study personnel within 30 to 45 minutes after EP, as well as at the follow up visits.

6.2.3.3 Vital Signs

Vital signs including oral temperature, respiration rate, blood pressure and heart rate will be measured at specified visits.

6.2.3.4 Weight and Height

Weight (kg) and height (cm) will be collected at screening.

6.2.3.5 12-Lead ECGs

An ECG will be performed at screening for all participants to determine eligibility. The ECG should include measurements of ventricular rate, PR, QRS, QT, QT_c with assessment as to whether the ECG is normal or abnormal. Abnormal ECGs will be interpreted as clinically significant or not clinically significant. Dosing will be delayed in the event of a clinically significant abnormal pre-dose ECG until it has been reviewed by the PI, qualified PI designee, Medical Monitor or Sponsor consultant cardiologist and deemed safe to proceed.

6.2.3.6 Laboratory Evaluations

At screening, Week 1, Week 6, and Week 14 (as indicated) blood samples will be taken to be tested for serum chemistry and hematology. Approximately 425 mL of blood will be drawn from each participant during the entire duration of the study.

Hematology

CBC: White blood cell (WBC) count and differential count, Red blood cell (RBC) count, Hemoglobin, Hematocrit, Platelet count;

Serum Chemistry

Serum electrolytes, blood urea nitrogen (BUN), creatinine (Cr), glucose, ALT, AST, CPK;

Serology (screening only):

Antibody to HIV (human immunodeficiency virus), Hepatitis B surface antigen (HBsAg), Hepatitis C antibody (HCV Ab), and West Nile virus, chikungunya virus, and dengue virus antibodies;

Pregnancy Test

For female participants of reproductive potential, a serum pregnancy test will be obtained at screening with a negative result. Participants who have a screening pregnancy test that is positive will be considered as ineligible for the study. If a pregnancy test is positive prior to completing the prescribed regimen, additional doses of vaccine must not be given. Every attempt should be made to follow pregnant participants for the remainder of the study and to determine the outcome of the pregnancy and to follow the outcome post-delivery for a year.

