Study Design:

This Phase I clinical trial will evaluate whether GLS-5700 administered via ID injection and followed by electroporation (EP) is safe, tolerated and able to generate an immune response against Zika virus in dengue virus-naïve participants and whether immune reactivity is dose-dependent. Injections will be given in the deltoid muscle followed immediately by EP with the CELLECTRA®-3P device.

GLS-5700 contains plasmid pGX7201 that encodes for a consensus sequence of the pre-membrane (prM) and envelope (E) proteins of Zika virus.

Currently there are no approved treatments or prophylactic vaccines for Zika virus. Nor have any vaccine candidates for Zika virus been advanced into human trials.

Evaluation of ID administration of GLS-5700:

There are two arms for ZIKA-001. Participants (n=20 per group) will be administered GLS-5700 at one of two dose levels: 1 mg or 2 mg DNA/dose. Vaccine will be administered as 0.1 ml ID injections followed by EP with the CELLECTRA®-3P device. Participants will receive one or two injections into the deltoid region at vaccination at 0, 4, and 12 weeks (3 vaccination series).

Safety assessment: Participants will be monitored for adverse events utilizing the “Toxicity Grading Scale for Healthy Adult and Adolescent Volunteers Enrolled in Preventive Vaccine Clinical Trials (Appendix B)” with labs assessed as per site normal values. Pain will be assessed immediately after EP and at 30 minutes post-EP. Laboratory safety assessments will be obtained at screening, 1 week following the 1st vaccination, and 2 weeks following the 2nd and 3rd vaccinations. Adverse events, including assessment of injection site reactions, will be monitored through 12 months after the final vaccination.

In the event that a stopping criterion is reached (Section 7.3.2), the study will not continue until a full discussion has been conducted with the Medical Monitor, Principal Investigator, and IRB/CER (if applicable).

Immunogenicity assessment: Blood will be obtained for Zika immune responses at baseline; at weeks 1, and 4; at 2 and 8 weeks following the 2nd and 3rd vaccinations; and at study weeks 36 and 60. Serum will be separated and sent for analysis for humoral responses (neutralizing and binding antibody titers). Whole blood will be processed to obtain peripheral blood mononuclear cells (PBMC) for ELISpot and/or ICS analysis.

Study Population:

Inclusion Criteria:

- a. Age 18-65 years;

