Serum ^g		X		X	X	X	X	X	X	X	
PBMCs ^g		X		X	X	X	X	X	X	X	
Blood Vol. per visit (mL)	15	70		80	70	80	70	80	70	70	70
Study Related Procedures											
Vaccine + EP		X			X		X				
EP Data ^h		X			X		X				
Memory aid ⁱ		X			X		X				
AEs		X	X ^j	X	X	X	X	X	X	X	X

^a Travel history to Central America, South America, Caribbean Islands, and South Pacific Islands at any time in past

^b Prior and concomitant, new medications will be recorded at all study visits (Day 0 through study discharge)

^c Full physical examination performed at screening and last visit or early termination only; perform targeted examinations at other visits as determined by Investigator or per participant complaints; record history of weight lifting or other significant physical activity; Vital signs will be performed pre and post vaccination at week 0, 4, and 12 week visits; height and weight will be recorded at screening.

^d Sodium (Na), potassium (K), chloride (Cl), bicarbonate (HCO₃), glucose, BUN, Cr, ALT, AST, CPK

^e HIV antibody or rapid test, HBsAg, HCV antibody, dengue, West Nile, and chikungunya virus antibodies

^f Serum pregnancy test at screening and urine pregnancy test thereafter

^g Collect **4 tubes** whole blood in ACD (yellow top) tubes for PBMCs; and 3 tubes of whole blood (red top) to obtain ~10 mL serum at the indicated time points

^h Download EP data within 48 hours of dose and transfer to GeneOne or its designee

ⁱ Provide memory aid to study participants and review on next visit

^j Detail AEs assessed via telephone.

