1.4 Risks/Benefit Assessment

In accordance with the International Conference on Harmonisation (ICH), this study has been designed to minimize risk to study participants. Potential risks of study products and administration from studies using similar plasmids with the identical DNA backbone are listed in **Table 1.4**.

The potential side effects of treatment with the investigational products may include but not limited to discomfort related to the vaccine administration and electroporation technique such as local edema, swelling, or pain. Systemic side effects observed with vaccines based on the identical backbone have been demonstrated to be generally minimal in more than 725 participants. Since the volunteers in this clinical trial have unknown risk for exposure to Zika virus, no direct benefit is expected. The potential benefit is to determine whether this vaccine could generate immune responses with potential to be sufficient as prophylactic treatment for those at risk for Zika virus infection.

Table 1.4: Summary of Reported Adverse Events of DNA Vaccines Delivered IM+EP or ID+EP with CELLECTRA®

Common	
 Mild to moderate administration site pain, erythema, tenderness, swelling, induration Malaise/fatigue, myalgia, or headache in the first few days following injection Visible lesion(s) at the injection site, such as erythematous papules with eschar, hypopigmentation, hyperpigmentation, or scar (ID administration only)
Less common	
 Administration site bruising/ecchymosis, hematoma or pruritus Arthralgia or nausea Injection site hematoma, bruising/ecchymosis, laceration, other transient lesions, or bleeding related to the injection procedure
Uncommon or rare	
 Administration site, laceration, other transient lesions, or bleeding related to the injection procedure Severe administration site pain or tenderness Rash following injection/EP Scar formation (ID administration) Vasovagal reaction/lightheadedness/dizziness related to the injection/EP procedure Transient changes in clinical laboratory values

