3. STUDY DESIGN

This is a Phase I open-label, dose-ranging study to assess the safety, tolerability, and immunogenicity of GLS-5700 in dengue virus-naïve adults. Eligible participants who consent to participate will be administered GLS-5700 via ID injection followed immediately by EP using the CELLECTRA® 3P Adaptive Constant Current Electroporation device.

Prospective participants who read and sign the ICF will be screened for eligibility for up to 30 days prior to their first dose. Screening evaluation will consist of a medical history, vital signs including height and weight, ECG, and laboratory evaluations. Participants without a history of exclusionary conditions, not clinically significant or normal ECG, and Grade 0-1 laboratory values (per the Toxicity Grading Scale for Healthy Adults Appendix B) for CBC, serum chemistry, and CPK, will be eligible for participation in the trial.

Evaluation of ID administration of GLS-5700:

Group 1 Participants (n=20) will be administered 1 mg GLS-5700 DNA/dose given as an ID injection followed by EP with the CELLECTRA®-3P device. Participants will receive a 3-dose series with immunizations at 0, 4, and 12 weeks.

Group 2 Participants (n=20) will be administered 2 mg GLS-5700 DNA/dose given as two ID injections per immunization followed by EP with the CELLECTRA®-3P device. Participants will receive a 3-dose series with immunizations at 0, 4, and 12 weeks.

See **Tables S1 and S2** for a summary of study treatments and dosing schedule.

Safety assessments: All participants will be monitored for

- Local and systemic adverse events (AE's) at each study visit.
- Laboratory related AE's following each vaccination.

Immunogenicity assessments:

The study will explore humoral and cell mediated immune responses in blood samples collected at the following times:

- Day 0 (prior to 1st dose of vaccine)
- Week 1 and week 4 post 1st vaccination
- Week 6 and 12 (2 and 8 weeks post 2nd vaccination)
- Week 14 and 20 (2 weeks and 8 weeks post 3rd vaccination)
- Weeks 36 and 60

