6.8.4 Flow Cytometry

Additional assessment of cellular immune activity may be performed via flow cytometry if sample volumes allow. Flow cytometric assays will include an examination of the influence of vaccination on the ability of patient T cells to exhibit phenotypic markers associated with cytolytic potential after short-term stimulation by Zika virus (hereafter referred to as “CTL Phenotyping”), the ability of patient T cells to remain active in the presence of long-term antigen exposure and efficiently synthesize proteins used in lytic activity (hereafter referred to as “Lytic Granule Loading”), and the ability of patient T cells to effectively employ Granzyme B for the purposes of lytic degranulation and killing of target cells expressing the S antigen (hereafter referred to as “Killing”). These panels may vary as new information becomes available. CTL Phenotyping will be prioritized while Lytic Granule Loading and Killing will only be run if sufficient patient samples are present.

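### The stated whole-study blood volume of about 425 mL conflicts with the Schedule of Events, whose visits sum to 675 mL

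*Protocol*

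**What the plan says.** Protocol Section 6.2.3.6 lists the safety laboratory draws (screening and Weeks 1, 6 and 14) and then gives a total for the whole study: "Approximately 425 mL of blood will be drawn from each participant during the entire duration of the study".

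Table S2 in the protocol synopsis has its own row of volumes by visit: "Blood Vol. per visit (mL) 15 70 80 70 80 70 80 70 70 70". In column order these are screening, Day 0, and Weeks 1, 4, 6, 12, 14, 20, 36 and 60. Day 1 is blank because it is a telephone contact. SAP Section 3.9 reproduces the same row.

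Three places support blood collection at the last visit. The synopsis schedules immune sampling "at 2 and 8 weeks following the 2nd and 3rd vaccinations; and at study weeks 36 and 60". Protocol Section 3 lists "Weeks 36 and 60". Section 6.1.2.4, on the Week 60 visit, includes "Collect blood for serum or PBMCs for immune assessment as indicated".

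**The concern.** The stated total and the schedule describe the same quantity, blood drawn per participant over the study, and they differ by far more than the word *approximately* can cover. The total is a burden figure for volunteers for whom, in the words of Section 1.4, "no direct benefit is expected". Someone who relies on Section 6.2.3.6, for example an ethics reviewer or an investigator, takes away a much smaller burden than someone who adds up Table S2. The consent form was not available for this review, so whether it repeats 425 mL cannot be checked.

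**Working it through.** **Inputs**
- Stated total: about 425 mL (Protocol 6.2.3.6).
- Scheduled volumes in mL (Table S2): screening 15, Day 0 70, Week 1 80, Week 4 70, Week 6 80, Week 12 70, Week 14 80, Week 20 70, Week 36 70, Week 60 70.

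**Sum over all visits**

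15 + 70 + 80 + 70 + 80 + 70 + 80 + 70 + 70 + 70 = 675 mL.

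Gap: 675 − 425 = 250 mL, and 250/425 = 58.8%.

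**Attempts to recover 425 mL**

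1. *Omit Week 60.* In the table as extracted, the serum and PBMC rows carry no mark at Week 60, so this was tested. 675 − 70 = 605 mL; 605 − 425 = 180 mL; 180/425 = 42.4%.
2. *Omit screening.* 675 − 15 = 660 mL.
3. *Stop at some visit.* Running totals:

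| Visit | Cumulative mL |
|---|---|
| Screening | 15 |
| Day 0 | 85 |
| Week 1 | 165 |
| Week 4 | 235 |
| Week 6 | 315 |
| Week 12 | 385 |
| Week 14 | 465 |
| Week 20 | 535 |
| Week 36 | 605 |
| Week 60 | 675 |

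   The total passes from 385 to 465 mL between Weeks 12 and 14 and does not land near 425. After Week 14, 3 × 70 = 210 mL remain.
4. *Count only one kind of draw.* The nine immune draws at 70 mL give 9 × 70 = 630 mL. If the extra 10 mL at Weeks 1, 6 and 14 is safety-laboratory blood (an inference from the table), safety blood is 15 + 3 × 10 = 45 mL. Neither matches.
5. *Any combination of visits.* No subset of the ten draws sums to 425. The nearest sums are 420 mL (6 × 70), 430 mL (5 × 70 + 80) and 435 mL (15 + 6 × 70). Each leaves out three or four of the ten draws. The 420 and 435 mL sums drop Weeks 1, 6 and 14 altogether, which Section 6.2.3.6 itself names as blood-draw visits.

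Footnote g of Table S2 gives tube counts (four for PBMCs, three for serum) but no tube volumes, so it cannot show which figure is intended.

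**The case against.** The best reply is that Table S2 plainly governs. Section 6 refers to it for procedures and their timing, Section 4.4 for immune samples and Section 6.4 for safety blood. The 425 mL figure appears once, as a summary, and no procedure depends on it. On that reading it is simply a total that was never updated. The true per-visit volumes are printed in the synopsis for anyone to add, the documents set no cap that is exceeded, and the analysis is untouched. This stands as an argument about weight and about the likelier remedy. It does not remove the conflict, because the understated total still sits in a procedures section and claims to cover the entire study.

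It is also fair to say that the missing Week 60 marks are probably a layout or extraction effect. The medication, physical examination and vital-sign rows lack them too, although Section 6.1.2.4 requires all three at that visit. The 605 mL figure is therefore only a robustness check, and 675 mL is the better-supported schedule total.

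Finally, nothing in the documents suggests that the sponsor means to cut the draws. The consequences of doing so are conditional and say nothing firm about assay adequacy, since no minimum assay volumes are given.

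**Conclusion.** The conflict is real. The schedule implies 675 mL against a stated 425 mL, a difference of 250 mL (59% of the stated figure), and the difference is still 180 mL (42%) if Week 60 is excluded. The result needs only addition of the printed row and assumes a participant who attends every visit. The SAP row is a copy of the protocol schedule, so it carries the same conflict and is not separate confirmation. The documents give Table S2 the operative role but nowhere say how 425 mL was obtained or which figure is meant. This is a clear error in a participant-burden figure that should be corrected. It does not threaten the validity of the trial.

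**What to change.** Reconcile Section 6.2.3.6 with Table S2.

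- **If Table S2 is what sites will follow:** restate the total as about 675 mL, counting the Week 60 serum and PBMC draw, and correct the consent form if it repeats 425 mL. The cost is one sentence, plus any consent wording. Endpoints, analyses and sample size do not change.
- **If about 425 mL is intended:** Table S2 and SAP Section 3.9 must be revised, which is more than a wording change. It would remove 250/675 = 37.0% of scheduled blood. As an illustration, keep the inferred 45 mL of safety blood and spread the cut evenly over the nine immune draws: (425 − 45)/9 = 42.2 mL per draw instead of 70 mL. The sponsor would then have to show that serum and PBMC supply still serves the secondary immunologic endpoints. The optional flow cytometry is already contingent on supply: "Additional assessment of cellular immune activity may be performed via flow cytometry if sample volumes allow".
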